11.2.2 Storage and Stability

Dexamethasone solution is stable at room temperature for 30 days after opening per package insert.

11.2.3 Compatibility

N/A

11.2.4 Handling

There are no special handling requirements.

11.2.5 Availability

Dexamethasone 0.5mg/5mL solution will be dispensed through the BWH Investigational Pharmacy.

11.2.6 Preparation

Study subjects will be given a kit with the following, including detailed written instructions (see Appendix 1):

CONFIDENTIAL

This document is confidential. Do not disclose or use except as authorized.

ARM B

- A four week supply of dexamethasone solution will be dispensed, with extra for error and spillage, which will be rounded to 480 mL bottle at a concentration of 0.5 mg/5mL.
- Small dosing cups

11.2.7 Administration

Subjects will be instructed to rinse with 5 ml of the prescribed dexamethasone 0.5mg/5ml solution (ARM B) for 5 minutes. After 5 minutes, subjects will be instructed to expectorate and to not eat or drink for 15 minutes after. The rinses will be completed three times per day, equally spaced during awake hours. If a study rinse is missed, subjects will be asked to attempt to make up for the missed rinse later the same day, to maintain four rinses per day. If necessary, for example, two consecutive 5 minute rinses can be completed at night before bed. This does not pose any known safety risk.

11.2.8 Ordering

Dexamethasone solution will be ordered through the BWH Investigational Pharmacy via EPIC.

11.2.9 Accountability

A study diary will be given to the subject where they will be asked to check off each rinse completed, with three check boxes per day on study (Appendix 2).

11.2.10 Destruction and Return

Patients should not continue to use any unused study supply once they have completed the study. It should be returned to the investigator for destruction.

12. DATA REPORTING / REGULATORY REQUIREMENTS

Adverse event lists, guidelines, and instructions for AE reporting can be found in Section 10.0

12.1 Monitoring and quality assurance

Safety monitoring

The safety of participants and the overall study will be monitored continuously throughout the study period. Evaluating physicians will query participants for any adverse events and review self-reported adverse events. Subjects will be instructed to contact their treating physician by phone or email to report any unexpected side effects or side effects lasting more than 7 days, should they occur. Any necessary medical intervention will be handled by the treating physician. Data accuracy and protocol compliance will be monitored and assured by the Principal Investigator and toxicities will be reported promptly to the IRB (see above).

CONFIDENTIAL

This document is confidential. Do not disclose or use except as authorized.

Appendix 1: Patient instructions

Appendix 2: Treatment diary

Appendix 3: Visit #1 CRF

Appendix 4: Visit #2 CRF

Appendix 5: COMDQLQ

CONFIDENTIAL

This document is confidential. Do not disclose or use except as authorized.

INSTRUCTIONS FOR PREPARING & USING YOUR TOPICAL SOLUTION

WHAT YOU WILL RECEIVE

- One 480 mL bottle of concentrated solution (5 mg/5 mL)

USING YOUR SOLUTION

You will be rinsing with your solution **3 times per day**.

1. Gently shake the bottle of solution.
2. Pour 5 mL of solution into the dosing cups provided.
3. Swish the solution in your mouth for 5 minutes, then spit – DO NOT SWALLOW!
4. Do not eat or drink for 15 minutes after rinsing.

CONFIDENTIAL

This document is confidential. Do not disclose or use except as authorized.

	13								
	14								

Week	Day/Date	Rinse #1 (check/fill)		Rinse #2 (check/fill)		Rinse #3 (check/fill)		From a scale 0-10, how would you rate your mouth sensitivity today?	Comments
		5 min	Other*	5 min	Other*	5 min	Other*		
3	15								
	16								
	17								
	18								
	19								
	20								
	21								
4	22								
	23								
	24								

CONFIDENTIAL

This document is confidential. Do not disclose or use except as authorized.

	25								
	26								
	27								
	28								

CONFIDENTIAL

This document is confidential. Do not disclose or use except as authorized.

**DEXAMETHASONE RINSE AND MUCOLOX™ FOR THE TREATMENT OF ORAL
LICHEN PLANUS**

VISIT #1

Subject Name _____

Medical Record Number _____

Date of Visit _____

[figure not shown]
[figure not shown]
SUBJECTIVE DATA (Over last two weeks unless specified)

MUCOSAL PATHOLOGY

1. Does your mouth hurt now? Y/N

2. Does it hurt to swallow food or drink? Y/N

3. How would you rate your worst mouth sensitivity over the last week?

No sensitivity

Worst sensitivity

CONFIDENTIAL

This document is confidential. Do not disclose or use except as authorized.

[figure not shown]
[figure not shown]
4. Do you avoid any foods because they make your mouth hurt?

- 0 = Not at all
- 1 = Slightly
- 2 = Moderately
- 3 = Quite a bit
- 4 = Extremely

If “yes”, what types of foods?

- a. Spicy foods
- b. Acidic foods
- c. Salty foods
- d. Hard/crunchy/crusty foods
- e. Other:

5. Do you feel that your oral intake (what you eat) is limited by your oral condition? Y/N

Not limited at all

Severely limited

Score: _____

If “Yes”, how limited do you feel it is?

- a. Partial limitation
- b. Severe limitation

6. Have you been bothered by ulcers in the mouth?

- 0 = Not at all
- 1 = Slightly
- 2 = Moderately
- 3 = Quite a bit
- 4 = Extremely

CONFIDENTIAL

This document is confidential. Do not disclose or use except as authorized.

OBJECTIVE DATA (REU score)

Site	Reticular area			Erythematous area			Ulcerative area				
	0	1		0	1	2	3	0	1	2	3
Upper/lower labial mucosa	0	1		0	1	2	3	0	1	2	3
Right buccal mucosa	0	1		0	1	2	3	0	1	2	3
Left buccal mucosa	0	1		0	1	2	3	0	1	2	3
Dorsal tongue	0	1		0	1	2	3	0	1	2	3
Ventral tongue	0	1		0	1	2	3	0	1	2	3
Floor of mouth	0	1		0	1	2	3	0	1	2	3
Hard palate mucosa	0	1		0	1	2	3	0	1	2	3
Soft palate/tonsillar pillars	0	1		0	1	2	3	0	1	2	3
Maxillary gingiva	0	1		0	1	2	3	0	1	2	3
Mandibular gingiva	0	1		0	1	2	3	0	1	2	3
Total											

(R: 0 = not present, 1 = present; E & U: 0 = not present, 1 = <1cm², 2 = 1 - 3cm², 3 = >3cm²)

Total Score:

Total Weighted Score:

PHOTOGRAPHS TAKEN (circle): YES NO

CONFIDENTIAL

This document is confidential. Do not disclose or use except as authorized.

DEXAMETHASONE RINSE AND MUCOLOX™ FOR THE TREATMENT OF ORAL LICHEN PLANUS

VISIT #2

Subject Name _____

Medical Record Number _____

Date of Visit _____

[figure not shown]
[figure not shown]
SUBJECTIVE DATA (Over last one week unless specified)

MUCOSAL PATHOLOGY

1. Does your mouth hurt now? Y/N

2. Does it hurt to swallow food or drink? Y/N

3. How would you rate your worst mouth sensitivity over the last week?

No sensitivity

Worst sensitivity

4. Do you avoid any foods because they make your mouth hurt?

- 0 = Not at all
- 1 = Slightly
- 2 = Moderately
- 3 = Quite a bit
- 4 = Extremely

If “yes”, what types of foods?

[figure not shown]
[figure not shown]
- a. Spicy foods
- b. Acidic foods
- c. Salty foods

CONFIDENTIAL

This document is confidential. Do not disclose or use except as authorized.

- d. Hard/crunchy/crusty foods
- e. Other:

5. Do you feel that your oral intake (what you eat) is limited by your oral condition? Y/N

Not limited at all

Severely limited

Score: _____

[figure not shown]
[figure not shown]
If “Yes”, how limited do you feel it is?

- a. Partial limitation
- b. Severe limitation

6. Have you been bothered by ulcers in the mouth?

- 0 = Not at all
- 1 = Slightly
- 2 = Moderately
- 3 = Quite a bit
- 4 = Extremely

7. Rate your level of comfort while rinsing with the topical therapy:

Not uncomfortable at all

[figure not shown]
[figure not shown]
Very uncomfortable

Score: _____

CONFIDENTIAL

This document is confidential. Do not disclose or use except as authorized.

8. Rate the taste of the topical treatment:

[figure not shown]
[figure not shown]

Very good taste

Very bad taste

Score: _____

9. Rate how your mouth feels since starting topical therapy:

Mouth feels much better

Mouth feels much worse

Score: _____

10. Overall, since beginning topical therapy, my mouth is: (Check one)

- Very much better
- Moderately better
- A little better
- About the same
- A little worse
- Moderately worse
- Very much worse

CONFIDENTIAL

This document is confidential. Do not disclose or use except as authorized.

OBJECTIVE DATA

Site	Reticular area			Erythematous area			Ulcerative area			
	0	1	0	1	2	3	0	1	2	3
Upper/lower labial mucosa	0	1	0	1	2	3	0	1	2	3
Right buccal mucosa	0	1	0	1	2	3	0	1	2	3
Left buccal mucosa	0	1	0	1	2	3	0	1	2	3
Dorsal tongue	0	1	0	1	2	3	0	1	2	3
Ventral tongue	0	1	0	1	2	3	0	1	2	3
Floor of mouth	0	1	0	1	2	3	0	1	2	3
Hard palate mucosa	0	1	0	1	2	3	0	1	2	3
Soft palate/tonsillar pillars	0	1	0	1	2	3	0	1	2	3
Maxillary gingiva	0	1	0	1	2	3	0	1	2	3
Mandibular gingiva	0	1	0	1	2	3	0	1	2	3
Total										

(R: 0 = not present, 1 = present; E & U: 0 = not present, 1 = <1cm², 2 = 1 - 3cm², 3 = >3cm²)

Total Score:

Total Weighted Score:

PHOTOGRAPHS TAKEN (circle): YES NO

CONFIDENTIAL

This document is confidential. Do not disclose or use except as authorized.

COMDQLQ

	Not at all (0)	Slightly (1)	Moderately (2)	Considerably (3)	Extremely (4)
Pain and functional limitation					
How much do certain types of food/drink cause you discomfort (spicy food, acidic food)?					
How much does your oral condition cause you to limit the types of food/ drinks you consume?					
How much do certain food textures cause you discomfort (rough food, crusty food)?					
How much does your oral condition cause you to limit the textures of the food you consume?					
How much does the temperature of certain foods/drinks cause you discomfort?					
How much does your oral condition cause you to limit the temperature of the foods/ drinks you consume?					
How much does your oral condition lead to discomfort when carrying out your daily oral hygiene routine (brushing, flossing, mouthwash usage)?					
How much does your oral condition cause you to limit your daily oral hygiene routine (brushing, flossing, mouthwash usage)?					
How much does your oral condition lead to discomfort when wearing a denture (false teeth)?					
Medication and treatment					
How much do you feel you need medication to help you with activities of daily life (talking, eating, etc.)?					
How satisfied are you with the medication being used to treat your oral condition?					
How concerned are you about the possible side effects of the medications used to treat your oral condition?					
How much does it frustrate you					

CONFIDENTIAL

This document is confidential. Do not disclose or use except as authorized.

that there is no single standard medication to be used in your oral condition?					
How much does the use of the medication limit you in your everyday life (routine/the way you apply or take your medications)?					
How much does it bother you that there is no cure for your oral condition?					
Social and emotional					
How much does your oral condition you down?					
How much does your oral condition cause you anxiety?					
How much does your oral condition cause you stress?					
How much does the unpredictability your oral condition bother you?					
How much does your oral condition cause you to worry about the future (spread of the condition, possible cancer risk)?					
How much does your oral condition make you pessimistic about the future?					
How much does your oral condition disrupt social activities in your life (social gatherings, eating out parties)?					
Patient support					
How satisfactory do you consider the information available to you regarding your oral condition?					
How satisfied are you with the level of support and understanding shown to you by family regarding this oral condition?					
How satisfied are you with the level of support and understanding shown to you by friends/work colleagues regarding your oral condition?					
How isolated do you feel as a result of this oral condition?					

CONFIDENTIAL

This document is confidential. Do not disclose or use except as authorized.

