5.2 Treatment Regimen

A four week supply of compound dexamethasone 0.5mg/5ml solution in Mucolox™ (Arm A) and dexamethasone 0.5mg/5ml solution (Arm B) will be dispensed. The treatment instructions will be to rinse and spit (NOT swallow) with one teaspoon (5 mL) of solution, three times a day for 5 minutes at a time, and not to eat or drink for 15 minutes afterwards. Subjects will maintain a diary and record each dose, the length of time rinsing, and any adverse effects (e.g. transient burning).

Regimen Description						
	Agent	Premedications; Precautions*	Dose	Route	Schedule	Cycle Length
Arm A	Dexamethasone in Mucolox™	None	5mL x 0.1mg/mL = 0.5 mg/rinse, 3 times/day =1.5 mg	Oral Rinse, 5 mins. each time (do not swallow)	7 days/week	28 days (4 weeks) One Cycle Only*

CONFIDENTIAL

This document is confidential. Do not disclose or use except as authorized.

Arm B (standard of care)	Dexamethasone solution	None	5mL x 0.1mg/mL = 0.5 mg/rinse, 3 times/day =1.5 mg	Oral Rinse, 5 mins. each time (do not swallow)	7 days/week	28 days (4 weeks) One Cycle Only*

*All subjects will be treated with antifungal dosing for prophylaxis (see section 5.5)

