8. RISKS AND DISCOMFORTS

8.1 Drug side effects and toxicities

Potential side effects with dexamethasone 0.5mg/5mL solution used as an oral topical rinse include an increased risk of developing oropharyngeal candidiasis and systemic absorption. All patients will be prescribed antifungal prophylaxis while on study with either fluconazole, clotrimazole or nystatin (see

CONFIDENTIAL

This document is confidential. Do not disclose or use except as authorized.

section 5.5). All participants will be informed that they may withdraw from the study at any time. As a topically applied agent, dexamethasone therapy can be discontinued at any time without any complications. Any noted clinical response will be expected to be reversed in such situations.

Prolonged application of potent topical corticosteroids (e.g., > 50 g of clobetasol propionate or > 500 g of hydrocortisone per week) may lead to short-term hypothalamic-pituitary-adrenal axis alteration. In our study, in case of any systemic absorption, the maximum dose would be 10.5 mg/week (5 mL x 0.1 mg/mL = 0.5 mg/rinse, 3 times/day = 1.5 mg, 7 days/week = 10.5 g). We do not expect there to be significant systemic absorption, and therefore do not expect systemic side effects of dexamethasone solution when used as a swish and spit. Mucolox™ is a vehicle for drug delivery used in compounding medications with ingredients expected to be harmless (see section 11.1.1).

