10.4 Expected Toxicities

A list of the adverse events and potential risks associated with the agents administered in this study appear above and will determine whether dose delays and modifications will be made or whether the event requires expedited reporting **in addition** to routine reporting.

Some expected toxicities include: transient burning, and the development of secondary oral candidiasis (which will be minimized with prophylactic antifungal drug therapy).

Prolonged application of potent topical corticosteroids (e.g., > 50 g of clobetasol propionate or > 500 g of hydrocortisone per week) may lead to short-term hypothalamic-pituitary-adrenal axis alteration³³. In our study, in case of any systemic absorption, the maximum dose would be 10.5 mg/week (5 mL x 0.1 mg/mL = 0.5 mg/rinse, 3 times/day = 1.5 mg, 7 days/week = 10.5 g). We do not expect there to be significant systemic absorption, and therefore do not expect systemic side effects of Mucolox™ and/or dexamethasone solution when used as a swish and spit.

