11.1.5 Preparation

Study subjects will be given a kit with the following, including detailed written instructions (see Appendix 1):

ARM A

- A four week supply of compound dexamethasone solution in Mucolox™ will be dispensed, with extra for error and spillage, which will be rounded to 480 mL bottle at a concentration of 0.5 mg/5mL.
- Small dosing cups

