11.1.6 Administration

Subjects will be instructed to rinse with 5 ml of compound dexamethasone solution in Mucolox™ (0.5 mg/5ml; ARM A) for 5 minutes. After 5 minutes, subjects will be instructed to expectorate and to not eat or drink for 15 minutes after. The rinses will be completed three times per day, equally spaced during awake hours. If a study rinse is missed, subjects will be asked to attempt to make up for the missed rinse later the same day, to maintain four rinses per day. If necessary, for example, two consecutive 5-minute rinses can be completed at night before bed. This does not pose any known safety risk.

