11.1.8 Accountability

A study diary will be given to the subject where they will be asked to check off each rinse completed, with three check boxes per day on study (Appendix 2).

CONFIDENTIAL

This document is confidential. Do not disclose or use except as authorized.

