11.2 Dexamethasone solution

11.2.1 Description

Dexamethasone (NDC 00054-3177-63; Roxane Laboratories, Columbus, OH 43216-6532) is a synthetic adrenocortical steroid commercially available as a 0.5mg/5mL solution. It is stable in air and practically insoluble in water.

- The molecular weight is 392.47.
- The molecular formula is $C_{22}H_{29}FO_5$
- The structural formula is:

Each 5 mL of oral solution contains 0.5 mg of dexamethasone and citric acid, disodium edetate, flavoring, glycerin, methylparaben, propylene glycol, propylparaben, sorbitol and water.

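### The patient instruction sheet gives ten times the specified rinse strength, and the missed-rinse clauses say four rinses a day where the regimen is three

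*Combined protocol and SAP*

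**What the plan says.** **Strength.** The Appendix 1 sheet describes the supply as "One 480 mL bottle of concentrated solution (5 mg/5 mL"). Sections 11.1.5 (Arm A) and 11.2.6 (Arm B) put this sheet in the kit and describe the same bottle, each with the words "which will be rounded to 480 mL bottle at a concentration of 0.5 mg/5mL". The regimen table in 5.2 works the dose out for both arms as "5mL x 0.1mg/mL = 0.5 mg/rinse, 3 times/day =1.5 mg". Section 11.2.1 says of the commercial product: "Each 5 mL of oral solution contains 0.5 mg of dexamethasone". Sections 5.3, 11.1.4 and 11.2.5 give the same strength.

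**Frequency.** Sections 11.1.6 and 11.2.7 first set three rinses a day. They then say that a subject who misses one should "attempt to make up for the missed rinse later the same day, to maintain four rinses per day". The accountability sections (11.1.8 and 11.2.9) describe a diary "with three check boxes per day on study", and the instruction sheet also says three.

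**Unit.** Sections 8.1 and 10.4 say that, if the drug were absorbed, "the maximum dose would be 10.5 mg/week". The bracketed arithmetic in the same sentence ends "7 days/week = 10.5 g".

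**The concern.** These figures stand in operative dosing instructions. The sheet is the document a patient keeps at home for four weeks. Section 5.5 confirms that there are no interim clinic visits, and section 10.1 has patients report side effects by phone, email or the patient portal. Anyone who takes the strength from the sheet, for example after a swallowed rinse or an adverse event, would put the dose ten times too high.

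The four-rinse wording conflicts with the prescribed daily dose and with the weekly maximum that the safety sections rely on. Both clauses add that making up rinses carries no known safety risk, so staff have little reason to question a fourth rinse. Adherence is judged from the diary and the returned bottles (5.4). The diary has no dedicated box for a fourth rinse, although its comments column could hold one, and a four-rinse target would blur the check on returned volume.

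**Working it through.** **Inputs**

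- Volume per rinse: 5 mL (5.2, 5.3, Appendix 1)
- Specified strength: 0.5 mg/5 mL = 0.1 mg/mL (5.2, 5.3, 11.1.4, 11.1.5, 11.2.1, 11.2.5, 11.2.6)
- Strength on the sheet: 5 mg/5 mL = 1 mg/mL (Appendix 1)
- Rinses per day: 3 (5.2, 5.3, diary, Appendix 1), or 4 (missed-rinse clauses of 11.1.6 and 11.2.7)
- Treatment period: 28 days (5.2)
- Bottle: 480 mL (11.1.5, 11.2.6, Appendix 1)

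**The plan's own figure.** Weekly dose = volume × strength × rinses per day × 7 = 5 × 0.1 × 3 × 7 = 10.5 mg. This reproduces the stated maximum exactly and shows that the unit in the bracket should be mg.

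**Which strength is right.** 5 / 0.5 = 10, so the sheet is tenfold out, and it is the only place that gives this figure. Could the bottle be a concentrate for dilution, as the word concentrated and the mention of preparing in the sheet's heading might suggest? Three points count against that:

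- The four steps on the sheet are to shake, pour 5 mL, swish and spit, and wait before eating or drinking. None dilutes anything.
- Sections 11.1.5 and 11.2.6 give the 480 mL bottle as dispensed at 0.5 mg/5 mL.
- 480 mL of a tenfold concentrate would make 480 × 10 = 4,800 mL of rinse, when 5 × 3 × 28 = 420 mL is needed.

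**Which frequency is right.**

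| | Three rinses/day | Four rinses/day |
|---|---|---|
| Daily dose | 0.5 × 3 = 1.5 mg | 0.5 × 4 = 2.0 mg |
| Weekly dose | 1.5 × 7 = 10.5 mg | 2.0 × 7 = 14 mg |
| Volume over 28 days | 15 × 28 = 420 mL | 20 × 28 = 560 mL |
| Days covered by 480 mL | 480 / 15 = 32 | 480 / 20 = 24 |

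Three rinses fit the bottle with a margin for spillage. Four rinses every day would empty it four days early. The supply was therefore sized for three.

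**Most that the four-rinse wording could add.**

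- Spare rinses = (480 − 420) / 5 = 12 beyond the 84 prescribed.
- Total drug in the bottle = 480 × 0.1 = 48 mg, against 84 × 0.5 = 42 mg prescribed.
- Average over four weeks = 48 / 4 = 12 mg/week, and 12 / 10.5 = 1.14, or 14% above the stated maximum.
- One week at four rinses a day uses 7 of the 12 spare rinses and gives 14 mg (14 / 10.5 = 1.33). The supply allows that for a week but not for all four.

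**If the sheet's strength were real.** 5 × 1 × 3 × 7 = 105 mg/week. No dispensing section supports this; the figure only shows what a reader of the sheet would calculate.

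**The case against.** The strongest reply is that little follows in practice. Everything the sheet asks the patient to do matches the regimen: 5 mL, three times a day, five minutes, then spit. The pharmacy dispenses at 0.5 mg/5 mL, so the wrong strength does not change the dose delivered, and the order in Epic is another source for the strength. The missed-rinse clause applies only when a rinse has been missed, and replacing one missed rinse restores three; the excess comes only from taking the word four literally. The patient's own sheet and diary say three. The 14 mg/week figure needs four rinses on every day of a week, which is unlikely.

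Most of this stands, and it limits the size of the point. The text is still wrong. A strength statement on a drug handout is there to be relied on when something goes wrong, and this one is wrong by a factor of ten. The clause sets a daily total that contradicts the sentence before it.

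The copy reviewed passes from the sheet to day 13 of the diary, so some appendix pages may be absent and a missing preparation step should not carry much weight. The conclusion does not depend on it, because 11.1.5 and 11.2.6 fix the strength of the bottle as dispensed.

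**Conclusion.** The concern holds and should be fixed. The sheet overstates the strength tenfold: 5 mg per rinse against 0.5 mg. The missed-rinse clauses in both arms, taken literally, permit 2.0 mg on a make-up day against 1.5 mg, with four-week exposure capped by the bottle at 48 mg against 42 mg. The gram unit in 8.1 and 10.4 is a minor slip, corrected by the mg figure in the same sentence.

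This rests on two readings, both well supported: that 0.5 mg/5 mL and three rinses a day are what is intended, and that one 480 mL bottle is each patient's whole supply. The documents do not show that anyone would receive the higher strength. The clause is worded identically in both arms, so it creates no planned difference between them. Sample size, endpoints and analysis are unaffected. So is the evaluability rule in 6.6, which depends on use falling below twice a day.

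**What to change.** - **Appendix 1:** delete the word concentrated and give the strength as 0.5 mg/5 mL. Remove the reference to preparing from the heading at the same time, since the rinse is ready to use.
- **11.1.6 and 11.2.7:** change four to three in the missed-rinse sentence.
- **8.1 and 10.4:** change 10.5 g to 10.5 mg.

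The 10.5 mg/week maximum then agrees with every dosing statement and needs no recalculation. The cost is a few words, an IRB amendment (section 6.3.2 brings participant materials under IRB review) and a reprinted sheet for the kits.
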